5.2.5.6 Management of fever in the absence of hypotension

- Administer antipyretics
- Adjust fluids to account for insensible losses if fever is persistent
- Obtain blood culture
- Administer empiric antibiotics if suggested by institutional policy

5.2.5.7 Management of treatment-related pain

- No further dinutuximab therapy should be given to patients who experience treatment related Grade 3 pain that cannot be controlled by narcotics during a given cycle. Treatment with gabapentin or similar agent should be initiated if not already being administered. If pain that is not controlled with narcotics recurs during a subsequent cycle, the patient should discontinue protocol therapy
- For patients with treatment-related Grade 3 pain requiring intravenous narcotics for ≥ 48 hours following completion of dinutuximab therapy, gabapentin or similar agent should be initiated if not already being administered. If pain requiring prolonged intravenous narcotics (≥ 48 hours following completion of dinutuximab therapy) recurs during a subsequent cycle despite this intervention, the patient should discontinue protocol therapy.

5.2.5.8 Management of visual changes

- Dinutuximab may cause impaired accommodation and/or dilated pupils with sluggish light reflex with or without photophobia. No dose modifications, dose reductions, or changes in infusion rate should be made unless there is associated vision loss. If this occurs in conjunction with Grade 3 decrease in vision, dinutuximab should be discontinued. If visual loss improves to Grade 1 or better before the next immunotherapy course is due, the patient should receive dinutuximab at a dose that is 50% reduced compared to the prior dose. Full dose sargramostim (GM-CSF) should be given. If the lower dose of dinutuximab is tolerated without worsening of ocular toxicity, full dose dinutuximab should be given in subsequent courses. If visual toxicity worsens, the patient should discontinue protocol therapy.
- Dose reductions for dilated pupils or changes in accommodation without vision loss are not required.

5.2.5.9 Management of serum sickness

- Identification of serum sickness – signs and symptoms include arthralgias/arthritis, splenomegaly, lymphadenopathy,

glomerulonephritis in the presence of persistent fevers, cutaneous eruptions.

- Serum sickness typically develops 1 to 3 weeks after administration of the causative agent, but can develop within 12-36 hours in patients who have previously been sensitized to the causative agent.
- Patients with \geq Grade 3 serum sickness should discontinue protocol therapy.
- For Grade 2 serum sickness, antihistamines should be prescribed.

5.2.5.10 Management of neurotoxicity

- Patients who develop Grade 4 neurotoxicity should discontinue protocol therapy.
- Dinutuximab should be discontinued for the remainder of the current cycle of therapy for patients who develop Grade 3 sensory neuropathy or Grade 3 motor neuropathy. If abnormalities resolve by start of next cycle of therapy, the patient may receive 50% dose of dinutuximab (i.e. dinutuximab dose 8.75 mg/m^2). If symptoms do not completely resolve or recur with dinutuximab then the patient should discontinue protocol therapy.

5.2.6 Management of sargramostim related toxicities

- Hold sargramostim if total white blood cell count is $> 50,000/\mu\text{L}$; resume at 50% dose when the count is $< 20,000/\mu\text{L}$. Administer full dose with subsequent cycles and modify again if the count exceeds $50,000/\mu\text{L}$
- Localized skin reactions to sargramostim are common, and sargramostim can be continued when reactions are mild. Rotation of sites of injections is recommended rather than use of insuflon for subcutaneous injection when skin reactions occur. Consider use of antihistamines. If \geq Grade 3 injection site reactions occur, stop sargramostim for the current cycle and discontinue sargramostim for subsequent cycles of therapy.
- A syndrome characterized by respiratory distress, hypoxia, flushing, hypotension, syncope, and/or tachycardia has been reported following the administration of the first dose of sargramostim in a particular cycle. This syndrome generally resolves with symptomatic treatment and usually does not recur with subsequent doses of sargramostim in the same cycle of treatment. For safety purposes in this study, if such a “first dose reaction” occurs, the sargramostim dose will be reduced to 50% for the next dose (i.e. sargramostim dose 125 mcg/m^2). If a similar reaction occurs at the 50% dose, the sargramostim will be discontinued for that patient. If the first dose at 50% does not cause any recurrent severe symptoms, subsequent doses can be escalated back to 100%. If recurrent severe symptoms are observed at 100% dose, then the dose will be reduced to 50%. If 50% is tolerated, that dose should be administered for all subsequent protocol treatment for that patient. If recurrent severe symptoms are seen at the 50% dose, the sargramostim will be discontinued for subsequent cycles of therapy.

5.2.7 Eflornithine (DFMO) specific dose modifications and toxicity management recommendations

5.2.7.1 Hearing Loss

Potential eflornithine-related hearing loss will be identified by audiologic assessment and defined as **≥ 15 dB increase from baseline in hearing threshold at two contiguous frequencies between 500 and 3000 Hz**. If this hearing deterioration is detected, eflornithine will be held for the remainder of the cycle and for one additional full cycle, and the audiologic testing should be repeated at the end of the entire dose holding period. If hearing sensitivity returns to pre-therapy baseline (or within 5dB of baseline), they will resume eflornithine at same dose. If hearing remains diminished as described above in comparison with pre-enrollment baseline, the eflornithine dose will be reduced by 25% (i.e. eflornithine of 5 g/m²/day as in [Appendix XII](#)) during the next cycle. Patients who have eflornithine held more than once for hearing loss, but return to baseline after hold, will have the eflornithine dose reduced by 25% for subsequent cycles. Patients who are receiving eflornithine at the lowest dose level (3750 mg/m²/day) for hearing loss and have recurrent or progressive hearing loss despite dose reduction will stop protocol therapy.

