5.2.1 Dose modifications for diarrhea

See [Appendix V](#) for patient/family instructions for supportive care measures for patients who develop therapy-associated diarrhea. Also included are specific instructions for loperamide dosing.

- If Grade 4 therapy-associated diarrhea is experienced by a patient with no evidence of infectious etiology and despite maximal use of anti-diarrheal medications and appropriate use of prophylactic antibiotics, the dose of irinotecan should be reduced by 25% for subsequent cycles (i.e. irinotecan dose 37.5 mg/m^2).
- If diarrhea persists despite maximal use of anti-diarrheal medications and appropriate use of prophylactic antibiotics for Grade 3 diarrhea > 7 days and Grade 4 diarrhea > 3 days after the completion of irinotecan, hold the eflornithine (DFMO) until diarrhea resolves to Grade 1. Then restart at prior dose.
- If Grade 4 therapy-associated diarrhea recurs without an infectious etiology despite reducing the dose of irinotecan by 25%, the dinutuximab dose (Arm A) or both the dinutuximab and eflornithine doses (Arm B) should also be decreased by 25% for subsequent cycles (i.e. dinutuximab dose $13.13 \text{ mg/m}^2/\text{day}$ and eflornithine dose $5 \text{ g/m}^2/\text{day}$ divided TID).
- If Grade 4 diarrhea recurs despite maximal use of anti-diarrheals, prophylactic antibiotics, and the dose reductions, the patient should come off protocol therapy.

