5.2.4 Dose modifications for elevations in ALT, AST, or GGT

- If elevations in ALT, AST or GGT occur such that values are $> 20x$ ULN for any duration of time OR $> 10x$ ULN but $< 20x$ ULN and persisting for > 7 days, the dose of dinutuximab should be reduced by 25% for subsequent cycles (i.e. dinutuximab dose 13.13 mg/m^2). For the purposes of this trial the ULN for ALT is defined as 45 U/L; institutional ULN values for AST and GGT should be used.
- If elevations of this magnitude involving same liver enzyme(s) recur despite the first dose reduction, the dose of temozolomide (Arm A) or eflornithine and temozolomide (Arm B) should be reduced by 25% for subsequent cycles (i.e. for temozolomide see dose reduction nomogram in [Appendix VII](#); eflornithine dose 5 g/m^2). If the dose limiting elevations of the same liver enzyme(s) recur despite the temozolomide/eflornithine dose reduction, the patient should come off protocol therapy.
- An elevation in ALT that causes a delay of ≥ 14 days between treatment cycles will also require a 25% reduction in the dose of dinutuximab for all subsequent cycles (i.e. dinutuximab dose 13.13 mg/m^2). If a delay of ≥ 14 days between treatment cycles recurs due to elevation in ALT despite the dose reduction, the patient should come off protocol therapy.

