5.2.7.2 Diarrhea occurring during single agent eflornithine lead-in (Days -6 to 1)

See [Appendix V](#) for patient/family instructions for supportive care measures for patients who develop therapy-associated diarrhea. Also included are specific instructions for loperamide dosing.

If eflornithine is stopped for any reason and then resumed at a lower dose, at least 5 days of the decreased dose of eflornithine should be given prior to starting Day 1 of the next cycle of chemotherapy, per [Section 5.2](#).

If Grade 4 therapy-associated diarrhea is experienced by a patient with no evidence of infectious etiology and despite maximal use of anti-diarrheal medications, the eflornithine dose should be held until diarrhea has resolved to Grade 1 or less and then restarted with a 25% reduction of the original dose (i.e. eflornithine of 5 g/m²/day).

If Grade 4 therapy-associated diarrhea recurs again without an infectious etiology and despite maximal use of anti-diarrheal medications, the eflornithine dose should be held again until diarrhea has resolved to Grade 1 or less and then decreased by an additional 25% (i.e. eflornithine of 3.75 g/m²/day).

If Grade 4 diarrhea recurs during single agent lead-in despite maximal use of anti-diarrheals, and the dose reductions, the patient should come off protocol therapy.

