APPENDIX XII: EFLORNITHINE (DFMO) DOSING TABLES

DOSE LEVEL – 6750 mg/m²/day (6.75 g/m²/day) divided TID					
BSA range (m²)		Dose 1 (g)	Dose 2 (g)	Dose 3 (g)	Total daily dose (g)
lower	upper				
0.35	0.40	1	1	0.5	2.5
0.41	0.47	1	1	1	3
0.48	0.55	1.5	1	1	3.5
0.56	0.62	1.5	1.5	1	4
0.63	0.69	1.5	1.5	1.5	4.5
0.70	0.77	2	1.5	1.5	5
0.78	0.84	2	2	1.5	5.5
0.85	0.92	2	2	2	6
0.93	1.03	2.5	2	2	6.5
1.04	1.21	2.5	2.5	2.5	7.5
1.22	1.43	3	3	3	9
1.44	1.66	3.5	3.5	3.5	10.5
1.67	1.88	4	4	4	12
1.89	and above	4.5	4.5	4.5	13.5

DOSE LEVEL – 5000 mg/m²/day (5 g/m²/day) divided TID					
BSA range (m²)		Dose 1 (g)	Dose 2 (g)	Dose 3 (g)	Total daily dose (g)
lower	upper				
0.35	0.47	1	0.5	0.5	2
0.48	0.55	1	1	0.5	2.5
0.56	0.63	1	1	1	3
0.64	0.77	1.5	1	1	3.5
0.78	0.84	1.5	1.5	1	4
0.85	0.92	1.5	1.5	1.5	4.5
0.93	1.03	2	1.5	1.5	5
1.04	1.21	2	2	1.5	5.5
1.22	1.43	2.5	2	2	6.5
1.44	1.66	2.5	2.5	2.5	7.5
1.67	and above	3	3	3	9

DOSE LEVEL – 3750 mg/m²/day (3.75 g/m²/day) divided TID					
BSA range (m²)		Dose 1 (g)	Dose 2 (g)	Dose 3 (g)	Total daily dose (g)
lower	upper				
0.35	0.47	0.5	0.5	0.5	1.5
0.48	0.63	1	0.5	0.5	2
0.64	0.77	1	1	0.5	2.5
0.78	0.84	1	1	1	3
0.85	1.03	1.5	1	1	3.5
1.04	1.21	1.5	1.5	1	4
1.22	1.43	2	1.5	1.5	5
1.44	1.49	2	2	1.5	5.5
1.50	1.88	2	2	2	6
1.89	and above	2.5	2.5	2	7

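### In 5.2.7.1 the 25% eflornithine cut for unrecovered hearing is printed only as 5 g/m²/day, so the step from 5 to 3.75 is not stated, and the stop rule misses some patients at 3750 mg/m²/day

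*Combined protocol and SAP*

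**What the plan says.** Section 5.2.7.1 holds eflornithine when audiology shows a shift of at least 15 dB from baseline at two contiguous frequencies. The hold covers the rest of the cycle and one further full cycle, and hearing is then retested. Three instructions follow.

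- Hearing still impaired: "the eflornithine dose will be reduced by 25% (i.e. eflornithine of 5 g/m²/day", with a pointer to Appendix XII. The sentence is not limited to patients on full dose.
- Repeat holds with recovery: patients "held more than once for hearing loss, but return to baseline after hold, will have the eflornithine dose reduced by 25" per cent. No resulting dose is printed.
- Stop rule: it applies to patients "receiving eflornithine at the lowest dose level (3750 mg/m²/day) for hearing loss and have recurrent or progressive hearing loss" despite the reduction; they stop protocol therapy.

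The lead-in diarrhoea rule in 5.2.7.2 prints both steps. The first is "restarted with a 25% reduction of the original dose (i.e. eflornithine of 5 g/m²/day"; at the second, the dose is "decreased by an additional 25% (i.e. eflornithine of 3.75 g/m²/day". Appendix XII tabulates 6750, 5000 and "3750 mg/m²/day (3.75 g/m²/day) divided TID".

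A patient can also be at 5 g/m²/day for reasons other than hearing. For recurrent Grade 4 diarrhoea, 5.2.1 says "both the dinutuximab and eflornithine doses (Arm B) should also be decreased by 25% for subsequent cycles". For recurrent liver-enzyme elevation, 5.2.4 says "the dose of temozolomide (Arm A) or eflornithine and temozolomide (Arm B) should be reduced by 25% for subsequent cycles". Both give 5 as the eflornithine result.

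**The concern.** One printed dose cannot be the result of a 25% cut from every starting level. For a patient already at 5, the percentage and the figure disagree, and a site must choose between them. The sentence on recovered patients carries no figure. Taken strictly by the printed dose, then, a patient at 5 who recovers after a second hold goes to 3.75, while one who does not recover stays at 5. That ordering cannot be intended.

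The stop rule depends on the same step. A patient whose loss persists reaches the hearing-loss stop only by first going from 5 to 3.75, and this branch does not print that move. The rule is also worded by the reason for being at 3750, so it leaves out a patient brought there by diarrhoea.

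Hearing loss is the toxicity for which this trial changed its eflornithine schedule. Section 2.5 reports Grade 3 loss in four of the first eight Regimen B patients with ototoxicity data, under continuous dosing. At stake is a child with unrecovered loss continuing on more drug than the rule intends. No analysis is at stake.

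**Working it through.** **Inputs.** Starting dose 6.75 g/m²/day (4.6.3); reduction 25% and printed result 5 (5.2.7.1); tabulated levels 6750, 5000 and 3750 mg/m²/day (Appendix XII); dosing on Days 1–7 and 15–21, so 14 days per cycle (4.7.3); audiograms at the end of Cycle 2 and every second cycle after that (4.7.2); at most six cycles from Amendment 4 (4.1).

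**The plan's own figure.** 6.75 × 0.75 = 5.06, listed as level 5. The actual cut is 1 − 5/6.75 = 25.9%. The printed figure is correct for a first reduction.

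**The same rule from the other levels (new dose = current dose × 0.75).**

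| Current dose (g/m²/day) | 25% cut | Appendix XII level | Printed figure |
|---|---|---|---|
| 6.75 | 5.06 | 5 | 5 (agrees) |
| 5 | 3.75 | 3.75 | 5 (conflicts) |
| 3.75 | 2.81 | none | 5 (cannot be a reduction) |

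**Size of the conflict at 5.** 5 − 3.75 = 1.25 g/m²/day; 5/3.75 = 1.33. In rounded Appendix XII daily doses, for example:

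| BSA (m²) | 5000 level (g/day) | 3750 level (g/day) | Difference (g/day) | Ratio |
|---|---|---|---|---|
| 0.35–0.47 | 2 | 1.5 | 0.5 | 1.33 |
| 0.48–0.55 | 2.5 | 2 | 0.5 | 1.25 |
| 0.64–0.77 | 3.5 | 2.5 | 1 | 1.40 |
| 1.67–1.88 | 9 | 6 | 3 | 1.50 |

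Over all BSA bands the difference is 0.5 to 3 g/day and the ratio 1.25 to 1.50. At BSA 0.70 m², one cycle is 14 × 3.5 = 49 g against 14 × 2.5 = 35 g.

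**How long it could last under Amendment 4.** These are illustrations on scheduled audiograms, not counting the five pre-cycle days after a hold.

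- *Hearing loss only.* Assume loss is found at the end of Cycle 2 and stable residual loss triggers a second hold. Cycle 3 is held, Cycle 4 given at 5, Cycle 5 held, and Cycle 6 given at 5 or 3.75. One cycle is affected: 14 × 1.25 = 17.5 g/m².
- *Already at 5 from lead-in diarrhoea.* Assume that reduction is kept, loss is found at the end of Cycle 2, and no further hold follows. Cycle 3 is held and Cycles 4–6 are given at 5 or 3.75: 3 × 14 = 42 days, 42 × 5 = 210 against 42 × 3.75 = 157.5 g/m². This is an upper bound. If stable residual loss triggers another hold, Cycle 5 drops out. It does not apply to a patient starting at 3.75.

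Patients enrolled before Amendment 4 could have up to 17 cycles, so more passes through the rule.

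**Stop rule, read against the routes to 3750.** A patient there for hearing loss whose loss recurs or worsens stops. A patient there after two lead-in diarrhoea reductions is not named by the rule, and 3.75 × 0.75 = 2.81 has no table. If that patient's first hearing loss fails to recover, it is also not clearly recurrent or progressive, so removing the qualifier alone would not settle the case.

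**The case against.** The strongest reply is that the operative instruction is the percentage and the figure only illustrates it. The same paragraph names 3750 as the lowest level for hearing loss, which a patient can reach for that reason only from 5. Appendix XII tabulates that level, and 5.2.7.2 prints the ladder in full. Section 5 regularly prints the full-dose result after a percentage (irinotecan 37.5, dinutuximab 13.13), and 5 is right for the commonest case.

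This stands as evidence of intent, and most sites would get to 3.75. It also rules out a stronger reading. A reader might infer that the protocol orders no cut for a patient at 5 and an increase for one at 3.75. The documents do not support that: an instruction to reduce cannot be read as leaving a dose unchanged or raising it, and a patient at 3750 for hearing loss whose loss recurs or worsens is told to stop.

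The reply does not remove the conflict. The sentence gives its figure as an equivalent, not an example, and eflornithine has two reduced levels, so one figure cannot serve both.

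Rarity and backstops also count. Section 2.5 gives Grade 3 loss below 5% with interrupted dosing and 1 of 24 in the similar neuroblastoma trial, although the hold here is triggered by a 15 dB shift, not by Grade 3. Reaching 3.75 through diarrhoea takes two Grade 4 episodes in the lead-in despite maximal treatment; Section 2.4 reports 3 of 24 patients with Grade 3 diarrhoea in that trial, none dose-limiting. The mandatory hold, regular audiograms, the monthly ototoxicity review (9.5) and removal for toxicity or physician judgement (8.1) limit harm. None of them states the next dose.

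**Conclusion.** The point holds as a dosing-clarity defect that should be corrected. The printed dose is right from 6.75. From 5, the percentage and the figure conflict by 1.25 g/m²/day, which is 25% to 50% more drug in rounded daily doses, and the intended step to 3.75 is missing from the branch for unrecovered hearing. Separately, a patient at 3750 because of lead-in diarrhoea has no lower level and no literal stop instruction.

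Under six cycles, the exposure affected is one cycle on the hearing-only route and at most three for a patient already at 5 from the lead-in, on the assumptions stated in the working. The documents do not give the number of patients affected; it is probably small. Sample size, power, type I error and endpoint definitions are unaffected.

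**What to change.** Three wording changes in 5.2.7.1:

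1. For hearing that has not recovered after the hold, replace the percentage and its bracketed figure with: one Appendix XII dose level below the current dose (6750 to 5000, or 5000 to 3750 mg/m²/day).
2. In the stop rule, delete the qualifier that ties the 3750 level to hearing loss.
3. Add that a patient already at 3750 for any reason stops if hearing has not recovered after a hold, or if loss recurs or progresses. This closes the case that the second change alone leaves open.

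The dose tables already exist, and no procedure or analysis is added. The cost is that a few patients receive less eflornithine or stop earlier. Under Section 5.0, stopping means ending all protocol therapy, although the backbone may continue as clinical care.

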5.2.7.2 Diarrhea occurring during single agent eflornithine lead-in (Days -6 to 1)

See [Appendix V](#) for patient/family instructions for supportive care measures for patients who develop therapy-associated diarrhea. Also included are specific instructions for loperamide dosing.

If eflornithine is stopped for any reason and then resumed at a lower dose, at least 5 days of the decreased dose of eflornithine should be given prior to starting Day 1 of the next cycle of chemotherapy, per [Section 5.2](#).

If Grade 4 therapy-associated diarrhea is experienced by a patient with no evidence of infectious etiology and despite maximal use of anti-diarrheal medications, the eflornithine dose should be held until diarrhea has resolved to Grade 1 or less and then restarted with a 25% reduction of the original dose (i.e. eflornithine of 5 g/m²/day).

If Grade 4 therapy-associated diarrhea recurs again without an infectious etiology and despite maximal use of anti-diarrheal medications, the eflornithine dose should be held again until diarrhea has resolved to Grade 1 or less and then decreased by an additional 25% (i.e. eflornithine of 3.75 g/m²/day).

If Grade 4 diarrhea recurs during single agent lead-in despite maximal use of anti-diarrheals, and the dose reductions, the patient should come off protocol therapy.

6.0 DRUG INFORMATION

[figure not shown]
See the consent document for toxicities. All other information is available on the COG website in the Commercial Agent Monographs (https://www.cogmembers.org/_files/disc/pharmacy/CommercialAgentsMonographs.pdf) and is provided under Standard Sections for Protocols at: <https://cogmembers.org/site/pages/default.aspx?page=Prot%20reference%20materials>.

6.1

A grid of 15 horizontal black bars of varying lengths and positions. The bars are arranged in three distinct horizontal bands. The top band contains four bars of increasing length from left to right. The middle band contains seven bars of uniform length. The bottom band contains four bars of increasing length from left to right. The bars are set against a white background.

A horizontal bar chart showing the distribution of 1000 samples across 10 categories. The x-axis represents the number of samples (0 to 1000) and the y-axis represents the category index (0 to 9). Categories 0, 1, 2, 3, 4, 5, 6, 7, 8, and 9 have 100, 100, 100, 100, 100, 100, 100, 100, 100, and 100 samples respectively. Category 10 has 100 samples.

Category	Number of Samples
0	100
1	100
2	100
3	100
4	100
5	100
6	100
7	100
8	100
9	100
10	100

A large block of black redacted text, consisting of approximately 25 lines of text, rendered as a solid black rectangle. The redaction is irregular, with some lines being completely black and others having small white gaps or breaks.

6.2 DINUTUXIMAB

(04/30/19)

(Unituxin®, MoAb 14.18, chimeric; human/murine anti-G_{D2} monoclonal antibody; chimeric anti-G_{D2}; chimeric mAb 14.18; ch14.18) NSC# 764038

Source and Pharmacology:

Dinutuximab (ch14.18, UTC) is an anti-G_{D2} monoclonal antibody composed of the variable region heavy and light chain genes of the murine mAb 14.G2a and the human constant region genes for heavy chain IgG₁ and light chain kappa. Dinutuximab exerts its antitumor effect by binding specifically to the disialoganglioside G_{D2}, an antigen found in human tumors of neuroectodermal origin such as melanoma and neuroblastoma. This chimeric antibody has been shown to lyse melanoma and neuroblastoma cells through the process of antibody-dependent cell-mediated cytotoxicity and complement-dependent cytotoxicity. By targeting the G_{D2} antigen on the cell surface, dinutuximab may also prevent attachment of circulating malignant cells to the extracellular matrix. Additionally, dinutuximab mediates lysis of several melanoma and neuroblastoma cell lines in a dose dependent manner in the presence of potent mediators of ch14.18-dependent cytotoxicity, such as human peripheral blood mononuclear cells and granulocytes. This is most profound with neutrophils, especially in the presence of recombinant human granulocyte-macrophage colony-stimulating factor.

The PK profile of dinutuximab has been determined in adults with melanoma and children with neuroblastoma. Although the plasma clearance for both groups of patients follow a two-compartment model, circulating antibody is cleared from the plasma at a much faster rate in children than adults (mean $t_{1/2}\beta = 66.6 \pm 27.4$ hours in children versus 123 ± 29 hours and 181 ± 73 hours in two adult trials, respectively). Maturation of the hepatic and renal systems with age is thought to impact on drug metabolism and elimination and could account for these differences. In general, the mAb half-life following the first course of treatment was longer than the half-lives following subsequent courses in a given patient.

Patient care implications:

Based on its mechanism of action, dinutuximab may cause fetal harm when administered to a pregnant woman. Advise pregnant women of the potential risk to a fetus. Advise females of reproductive potential to use effective contraception during treatment, and for two months after the last dose of dinutuximab.

It is not known if dinutuximab is excreted in breast milk. IgG molecules are excreted in breast milk. Due to the potential for serious adverse reactions in the nursing infant, breastfeeding is not recommended.

Toxicity:**Comprehensive Adverse Events and Potential Risks list (CAEPR)
for
Dinutuximab (MoAb 14.18, chimeric, NSCs 623408 and 764038)**

The Comprehensive Adverse Events and Potential Risks list (CAEPR) provides a single list of reported and/or potential adverse events (AE) associated with an agent using a uniform presentation of events by body system. *Frequency is provided based on 359 patients.* Below is the CAEPR for dinutuximab (MoAb 14.18, chimeric).

Version 2.9, January 10, 2019⁶⁰

Adverse Events with Possible Relationship to dinutuximab (CTCAE 5.0 Term) [n= 359]		
Likely (>20%)	Less Likely (<=20%)	Rare but Serious (<3%)
BLOOD AND LYMPHATIC SYSTEM DISORDERS		
	Anemia	
	Disseminated intravascular coagulation	
		Hemolytic uremic syndrome ⁶¹
CARDIAC DISORDERS		
		Cardiac arrest
		Sinus bradycardia
	Sinus tachycardia	
EYE DISORDERS		
		Eye disorders - Other (eye disorders) ⁶²
GASTROINTESTINAL DISORDERS		
	Abdominal pain	
	Diarrhea	
	Nausea	
	Vomiting	
GENERAL DISORDERS AND ADMINISTRATION SITE CONDITIONS		
	Edema limbs	
Fever		
	Generalized edema	
Pain		
		Sudden death NOS
IMMUNE SYSTEM DISORDERS		
	Allergic reaction	
		Anaphylaxis
	Serum sickness	

Adverse Events with Possible Relationship to dinutuximab (CTCAE 5.0 Term) [n= 359]		
Likely (>20%)	Less Likely (<=20%)	Rare but Serious (<3%)
INFECTIONS AND INFESTATIONS		
	Infection ⁶³	
		Myelitis ⁶⁴
INJURY, POISONING AND PROCEDURAL COMPLICATIONS		
		Infusion related reaction
INVESTIGATIONS		
	Alanine aminotransferase increased	
	Aspartate aminotransferase increased	
	Creatinine increased	
Investigations - Other (elevated c-reactive proteins)		
	Lymphocyte count decreased	
	Neutrophil count decreased	
	Platelet count decreased	
	White blood cell decreased	
METABOLISM AND NUTRITION DISORDERS		
	Anorexia	
	Hyperkalemia	
	Hypoalbuminemia	
	Hypocalcemia	
	Hypokalemia	
	Hyponatremia	
MUSCULOSKELETAL AND CONNECTIVE TISSUE DISORDERS		
	Back pain	
	Pain in extremity	
NERVOUS SYSTEM DISORDERS		
	Neuralgia	
		Peripheral motor neuropathy
	Peripheral sensory neuropathy ⁶⁵	
		Reversible posterior leukoencephalopathy syndrome
RENAL AND URINARY DISORDERS		
	Proteinuria	
		Renal and urinary disorders - Other (atonic urinary bladder) ⁶
	Urinary retention ⁶⁵	
RESPIRATORY, THORACIC AND MEDIASTINAL DISORDERS		
	Bronchial obstruction	

Adverse Events with Possible Relationship to dinutuximab (CTCAE 5.0 Term) [n= 359]		
Likely (>20%)	Less Likely (<=20%)	Rare but Serious (<3%)
Cough		
	Dyspnea	
	Hypoxia	
SKIN AND SUBCUTANEOUS TISSUE DISORDERS		
	Pruritus	
Rash maculo-papular		
	Urticaria	
VASCULAR DISORDERS		
	Capillary leak syndrome	
	Hypertension	
	Hypotension	

¹This table will be updated as the toxicity profile of the agent is revised. Updates will be distributed to all Principal Investigators at the time of revision. The current version can be obtained by contacting [contact]. Your name, the name of the investigator, the protocol and the agent should be included in the e-mail.

²There have been rare instances of atypical hemolytic uremic syndrome in the absence of documented infection and resulting in renal insufficiency, electrolyte abnormalities, anemia, and hypertension.

³Neurological disorders of the eye including blurred vision, diplopia, cycloplegia, mydriasis, photophobia, optic nerve disorder, eyelid ptosis, and fixed pupils have been observed.

⁴Infection includes all 75 sites of infection under the INFECTIONS AND INFESTATIONS SOC.

⁵Myelitis expressed as transverse myelitis has occurred in patients treated with dinutuximab. Symptoms may include weakness, paresthesia, sensory loss, or incontinence.

⁶Acute urinary retention occurs during therapy and is thought to be due to fluid shifts and narcotic administration that accompany dinutuximab administration. Atonic urinary bladder results in chronic urinary retention (CUR) that requires intermittent urethral catheterization days to weeks following dinutuximab administration.

Adverse events reported on dinutuximab trials, but for which there is insufficient evidence to suggest that there was a reasonable possibility that dinutuximab caused the adverse event:

BLOOD AND LYMPHATIC SYSTEM DISORDERS - Blood and lymphatic system disorders - Other (thrombotic microangiopathy [e.g., thrombotic thrombocytopenic purpura [TTP] or hemolytic uremic syndrome [HUS]]; Bone marrow hypocellular; Febrile neutropenia; Hemolysis

CARDIAC DISORDERS - Cardiac disorders - Other (gallop on exam); Cardiac disorders - Other (N-terminal BNP); Chest pain - cardiac; Heart failure; Left ventricular systolic dysfunction; Mobitz (type) II

atrioventricular block; Myocardial infarction; Palpitations; Pericardial effusion; Supraventricular tachycardia; Ventricular tachycardia

EAR AND LABYRINTH DISORDERS - Ear pain; Hearing impaired

ENDOCRINE DISORDERS - Endocrine disorders - Other (transient hypoaldosteronism); Hyperthyroidism; Hypothyroidism

EYE DISORDERS - Papilledema; Periorbital edema; Scleral disorder

GASTROINTESTINAL DISORDERS - Abdominal distension; Ascites; Cheilitis; Colitis; Constipation; Duodenal obstruction; Dysphagia; Enterocolitis; Esophageal stenosis; Esophageal ulcer; Esophagitis; Gastrointestinal disorders - Other (bleeding, NOS); Gastrointestinal disorders - Other (esophageal stricture); Gastrointestinal disorders - Other (ischemic bowel); Gastrointestinal disorders - Other (pneumatosis intestinalis); Gastroparesis; Hemorrhoidal hemorrhage; Ileus; Intra-abdominal hemorrhage; Lower gastrointestinal hemorrhage; Mucositis oral; Oral pain; Rectal hemorrhage; Stomach pain; Typhlitis
GENERAL DISORDERS AND ADMINISTRATION SITE CONDITIONS - Chills; Death NOS; Edema face; Edema trunk; Fatigue; General disorders and administration site conditions - Other (cold and clammy); General disorders and administration site conditions - Other (vascular leak syndrome); Hypothermia; Injection site reaction; Localized edema; Non-cardiac chest pain

HEPATOBILIARY DISORDERS - Hepatobiliary disorders - Other (cholestasis)

IMMUNE SYSTEM DISORDERS - Cytokine release syndrome

INJURY, POISONING AND PROCEDURAL COMPLICATIONS - Fracture

INVESTIGATIONS - Activated partial thromboplastin time prolonged; Alkaline phosphatase increased; Blood bilirubin increased; Cardiac troponin I increased; Cholesterol high; Ejection fraction decreased; Electrocardiogram QT corrected interval prolonged; Fibrinogen decreased; GGT increased; INR increased; Lipase increased; Lymphocyte count increased; Urine output decreased; Weight gain; Weight loss

METABOLISM AND NUTRITION DISORDERS - Acidosis; Dehydration; Hypercalcemia; Hyperglycemia; Hypermagnesemia; Hypernatremia; Hypertriglyceridemia; Hypoglycemia; Hypomagnesemia; Hypophosphatemia

MUSCULOSKELETAL AND CONNECTIVE TISSUE DISORDERS - Arthralgia; Arthritis; Bone pain; Chest wall pain; Muscle weakness lower limb; Myalgia; Neck pain

NERVOUS SYSTEM DISORDERS - Cognitive disturbance; Depressed level of consciousness; Dysesthesia; Dysgeusia; Dysphasia; Encephalopathy; Extrapyramidal disorder; Headache; Hydrocephalus; Meningismus; Movements involuntary; Nystagmus; Oculomotor nerve disorder; Paresthesia; Seizure; Somnolence; Syncope; Tremor

PSYCHIATRIC DISORDERS - Agitation; Anxiety; Confusion; Delirium; Hallucinations; Insomnia; Irritability; Personality change; Restlessness

RENAL AND URINARY DISORDERS - Acute kidney injury; Chronic kidney disease; Glucosuria; Hematuria; Renal and urinary disorders - Other (acute renal insufficiency); Renal and urinary disorders - Other (urethritis); Renal hemorrhage

REPRODUCTIVE SYSTEM AND BREAST DISORDERS - Hematosalpinx; Ovarian hemorrhage; Pelvic pain; Penile pain; Prostatic hemorrhage; Spermatic cord hemorrhage; Testicular hemorrhage; Uterine hemorrhage; Vaginal hemorrhage

RESPIRATORY, THORACIC AND MEDIASTINAL DISORDERS - Adult respiratory distress syndrome; Apnea; Atelectasis; Bronchospasm; Laryngeal edema; Laryngopharyngeal dysesthesia; Laryngospasm; Pharyngolaryngeal pain; Pleural effusion; Pleuritic pain; Pneumonitis; Pulmonary edema; Respiratory failure; Respiratory, thoracic and mediastinal disorders - Other (tachypnea); Stridor; Wheezing

SKIN AND SUBCUTANEOUS TISSUE DISORDERS - Dry skin; Erythema multiforme; Hyperhidrosis

VASCULAR DISORDERS - Flushing

Note: dinutuximab in combination with other agents could cause an exacerbation of any adverse event currently known to be caused by the other agent, or the combination may result in events never previously associated with either agent.

Formulation and Stability:

Dinutuximab is provided as a sterile solution in single-dose vials containing 17.5 mg/5 mL (3.5 mg/mL) in 20 mM Histidine, 150 mM NaCl, 0.05% Tween 20 at pH 6.8. Intact vials should be stored in the refrigerator at 2°C to 8°C (36°F to 46°F); do not freeze. Do not shake. Keep the vial in the outer carton to protect from light. Solutions diluted for infusion should be stored at 2°C to 8°C (36°F to 46°F). Initiate infusion within 4 hours of preparation. Discard diluted solution 24 hours after preparation.

Must be diluted prior to infusion. Withdraw the required dinutuximab volume and inject into a 100 mL bag of NS. Mix by gentle inversion; do not shake. Discard unused vial contents. Initiate infusion within 4 hours of preparation. Do not use if cloudy, discolored (pronounced), or contains particulates. The use of a filter during preparation is not required. The final prepared product of dinutuximab in NS is stable at room temperature for 24 hours when diluted to a concentration between 0.044 mg/mL and 0.56 mg/mL; however, the final dosage form should be prepared immediately prior to administration as there is a maximum infusion time of 20 hours.

Guidelines for Administration:

See Treatment, Dose Modifications and/or Supportive Care sections of the protocol.

Administer as an IV infusion only (the minimum dinutuximab infusion time is 10 hours up to a maximum of 20 hours); **do not administer as an IV push or bolus**. Administer NS 10 mL/kg IV over 1 hour just prior to each dinutuximab infusion. Premedicate with analgesics, an antihistamine, and an antipyretic prior to administration. Infuse in an environment equipped to monitor for and manage infusion reactions. Interrupt infusion for toxicity. Monitor patients closely for signs and symptoms of an infusion reaction during and for at least 4 hours following completion of each dinutuximab infusion.

Supplier:

Commercially available. See package insert for further information.

CANADIAN SITES:

Commercially available through McKesson Canada.

AUSTRALIA AND NEW ZEALAND SITES:

United Therapeutics will provide dinutuximab via expanded access program to the COG sites in Australia and New Zealand that had ANBL0032 study open in the past. Dinutuximab can only be used in accordance with the United States prescribing information. IDIS Managed Access will be utilized for this program. Prescribers can order dinutuximab for new patient starts by requesting a copy of updated IDIS patient access form at [contact]

